The HbA1C outcome was used for the sample size calculation. Since we are collecting HbA1C every 8 weeks, we are able to leverage the repeated measures design in the estimation of the sample size needed for this study. This allows us to gain efficiency and reduce the number of subjects needed. Thus, for an effect size 'f' of 0.14, which is between small (0.10) and medium (0.25), an alpha of 0.05 and power of 0.80, we need a total of 92 study subjects. Allowing for some attrition in study subjects, we are planning to enroll 100 patients.

Note that this type of sample estimation requires that we specify the variance across observations (sphericity) and the correlation across observations. We specified both at 0.60. We calculated sample size using G*Power.

Data Analysis Plan

The data analysis will start with completion of the **CONSORT** diagram, with an analysis of differences between those who completed the study and those who did not (t-tests and chi-square tests, as needed, comparing basic demographics and baseline health characteristics), so that the researchers in this area can understand the extent to which our study contains bias.

Next, we will calculate summary statistics (means, medians, proportions, etc.) of all baseline measurements, overall and by study arm, so that we can fully characterize the study cohort.

Using the CGM data, we will graph each participant's trajectories over time and review each, examining for major patterns in the trajectories. Note that typically statistical analyses emphasize homogeneity in the data; however, this approach will allow for understanding of heterogeneity. As part of this examination of the CGM data, the analysis will calculate each participant's measures of glycemic variability (such as mean amplitude of glycemic excursions, coefficient of variation, etc.), HbA1C values, and fructosamine values and overlay them on each graph. This part of the analysis is predominantly exploratory.

For the statistical, hypothesis-testing examinations of HbA1C, fructosamine, CGM readings, and glycemic variability across key time points, we will conduct mixed models (i.e., multilevel model) analyses, which will allow us to quantify within-between interactions, or changes within subjects over time and differences across groups. These models can also include multiple independent variables/covariates.

F. Inclusion/Exclusion Criteria

Inclusion criteria:

1. Pregnancy and Gestation \leq 30 weeks
2. Singleton pregnancy

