-HbA1C $\geq 6.5\%$ is diagnostic of pre-gestational DM. Diabetes education and therapy should be initiated as soon as possible and given pre-gestational DM will be excluded from the study

-HbA1C 6.0-6.4% may be considered diagnostic of GDM but confirmation testing with 3 hour glucose tolerance test is still considered standard of care. OB providers will ask patients to complete the 3 hour GTT. However, given potential exposure in 3-hour testing during the COVID-19 pandemic if patients decline then HbA1C $\geq 6.0\%$ will be used for enrollment

-HbA1c 5.7-5.9% should be considered concerning for impaired glucose tolerance. Local protocol is re-evaluation for GDM with a 3 hour GTT at 24-28 weeks. In this case, the 1 hour GCT is not recommended as the initial screen as these women have already been identified as being at elevated risk for GDM. If patients decline 3-hour testing and elect for HbA1c instead, then HbA1C $\geq 6.0\%$ may be used for enrollment.

-HbA1c $<5.7\%$ is normal; these women will have routine GDM screening at 24-28 weeks

Routine Screening & Diagnosis of GDM

We will use the 2 step protocol with oral glucose tolerance testing for diagnosis. For the glucola (50g) we will use a 1-hour cutoff of >140 or HbA1C $\geq 6.0\%$ followed by the 3 hour for confirmation of GDM per local protocol at UW.

A 1-hour GCT level of 180mg/dl will be considered diagnostic of GDM without proceeding to a 3-hour GTT. In select situations based on either clinician's assessment or patient's refusal to accept diagnosis based on the

GCT, a 3-hour GTT may be considered for GCT results between 180-200mg/dL. A follow up 3-hour GTT is not required for any patient with a GCT ≥ 200 mg/dL, as that value is sufficient for the diagnosis of GDM.

If the patient has an elevated glucola then the 100-g 3-hour GTT should be performed. This will include a fasting blood sugar, and a 1, 2, and 3-hour post GTT plasma glucose levels will be measured. The diagnosis of GDM is based if at least two of the four plasma glucose levels are met or exceeded using the Carpenter/Coustan criteria as outlined by the ADA (reference). The values are fasting 95 mg/dL (5.3 mmol/L), 1-hr 180 mg/dL (10.0 mmol/L), 2-hour 155 mg/dL (8.6 mmol/L), and 3-hour 140 mg/dL (7.8 mmol/L).

American Diabetes Association. 2. Classification and diagnosis of diabetes: *Standards of Medical Care in Diabetes—2020*. Diabetes Care 2020;43(Suppl. 1):S14–S31(11)

H. Study Design

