Vital signs will be collected, including height, weight (current and pre-pregnancy), blood pressure, maternal resting heart rate, and estimated gestational age. Maternal ultrasound results will be reviewed if available.

Glucose tolerance test results will be reviewed. Two blood pressure and pulse readings will be taken and HbA1c, both point of care (fingerstick) and HbA1c serum and fructosamine via LabCorp will be obtained. Approximately 1 teaspoon of blood will be drawn. If a patient has an HbA1c documented in the medical record within 2 weeks of the pre-intervention session, then the point of care HbA1c will not be done. The available HbA1c will be used. If they meet all inclusion and exclusion criteria (as outlined above), they will be randomized into either the RT-CGM intervention or control arm at the screening visit.

At the pre-intervention session (week 0) the control GDM group will be asked to wear the CGM blinded for 10 days. They will be asked to continue their usual diet and activity. If, for any reason, the CGM device fails to capture at least 3 days worth of data, the subject may be asked to repeat this measurement at an unscheduled visit. The control group will be given a glucose meter (onetouch) and instructed to follow their obstetric provider's recommendations about checking glucose by meter or if they have not been given instructions or do not remember their instructions they will be asked to check sugars fasting and 1 hour after meals. They will also be given a handout that explains glucose goals and how food and activity effects glucose levels. (Appendix A1,A2). The intervention group will be given RT-CGM and instructed on use with a handout that explains glucose goals and how food and activity effects glucose levels (see handout/Appendix A). The intervention group will also be given a glucose meter (onetouch) and instructed to use for symptoms of low glucose or if they question the accuracy of the CGM. Both groups will be given standard gestational diabetes teaching and nutrition counseling by the RN in clinic and with individual nutrition appointments with the nutritionist, as per current local standard of care.

Participants will be given self-report questionnaires on physical activity, nutrition, sleep history, pregnancy history and overall wellness. Week 0 consenting and baseline data/measurements will take between 1 hour 30 minutes and 2 hours.

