study visit 2 (with de-identified data) or it sends the information via wireless radio frequency to a monitoring/display device or to a cellular phone so one can see their own data on their glucose and we can download it remotely. The device automatically generates an alert for glucose < 55, and an alert will also be generated for glucose > 140 in the unblinded portion of the study. The intervention group participants will be given a handout (Appendix K) for troubleshooting these alerts, particularly during the blinded portion of the study. DEXCOM G6 is FDA approved for use in patients with diabetes and will be used in accordance with instructions as approved for diabetes. It is not currently approved for patients with gestational diabetes but will be used in accordance with instructions as approved for diabetes. The risk is minimal with use of this device. In this study, we recommend patients connect the CGM to their cell phones, but if unable/unwilling, we will provide transmitters for participants to allow for real-time monitoring. Study staff will insert the first sensor for the groups and demonstrate how to insert additional sensors for the intervention group who will continue to use RT-CGM. If this is to be done as a televisit, the sensors, transmitter, and device (if needed) will be mail to the participant. Then the study staff will walk the participant through the first insertion through a virtual zoom visit. Patients will also have a YouTube video available for reference for the patients. For the blinded control, the research coordinator will insert all sensors unless televisit is needed with procedure as above. The patients will be instructed on how to remove the sensor themselves after 10 days and bring back their scheduled OB visit. The intervention group will wear the RT-CGM continuously and change the sensor every 10 days for the duration of the pregnancy and have telephone support and may refer to the YouTube video on insertion if needed. The intervention participants will have RT-CGM download serially over the study during regularly scheduled OB visits or televisits. The control group participants will wear the blinded CGM at beginning, at 30-32 and 34-36 weeks of the study. If, during the blinded portion of the study, due to device malfunction (rather than subject non-compliance), the device records less than 3 days of data, the participant can return to restart another 10 days of blinded CGM data.

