The receiver and/or the app will display the glucose reading along with a rate of change arrow and a trend graph. Additionally, the receiver and/or app issues alarms and alerts to notify the patient of glucose level changes and other important system conditions. The app provides the additional capability to share data with “followers” using the Dexcom Share service. The receiver can be put into a blinded mode using CLARITY® software. In this mode, users are unable to see the CGM data or receive CGM alerts.

CGM Ancillary Devices Dexcom CLARITY® is an accessory for users of the Dexcom CGM system. It is a software program that allows the transfer of glucose data from the CGM system to Dexcom remote servers for data management to allow the use of the CGM data by the user and study clinicians. Target ranges of 65 to 140 mg/dl [3.6 to 7.8 mmol/l] will be set and the patients will be introduced to the use of alarm settings. Both participants and study sites will use CLARITY® to transfer glucose data between user and study site, whether CGM is used in blinded or real-time mode. A CLARITY® mobile app can be used for a retrospective review of glucose data on the smart device and can also be set up to allow receipt of push notifications of CGM data facilitating data review. For all patients (intervention and control group) an anonymized CLARITY® account will be created by using a sequential study number which is allocated at randomization.

Intervention Group:

- For participants who have a supported phone, the DEXCOM G6 CGM app will be installed on participant's smart phone.
- An anonymized CLARITY® mobile account will be set up and linked to the research site.
- Participants will use CGM data to log their blood sugars for fasting and 1-hour post-meals for review by their OB provider. The OB providers will not specifically use the CGM in their management decisions.
- A high alert threshold will be set at 140 mg/dl [7.8 mmol/l]. Low alert threshold and urgent low soon alerts will be turned off. If participants require insulin, the low alert will be turned on and the threshold set at 65 mg/dl [3.6 mmol/l]. In addition, the urgent low alert (55 mg/dl [3.1 mmol/l]), the urgent low soon alert (when glucose levels

are falling fast and will be below 55 mg/dl [3.1 mmol/l] in less than 20 min) as well as alerts for rise and fall rate (3 mg/dl [0.17 mmol/l]) in addition to alerts for signal loss and no readings for more than 20 min will be enabled.

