Perception/Satisfaction with CGM and Fingersticks/Meter (Appendices J): The Harvard Joslin Diabetes Center has developed a series of questionnaires on CGM experiences, opinions and expectations that will be given at the end of the intervention and has been adapted for the GDM. Additionally, questions about food changes and activity changes that was created for CGM use(19,20) . Questionnaires have been adapted for use in those using only meter fingersticks and for GDM.

Sleep Questionnaire (appendix Q) The Pittsburgh Sleep Questionnaire is good tool for screening sleep disorders in the population and has been used in pregnancy (22,23)

N: Glucose/CGM Data /Evaluation Measures: The compliance and duration wear for participants with CGM will also be recorded. Glucose dynamics, e.g., average glucose, standard deviation, mean amplitude of glucose excursion (MAGE), time in range % (65 and 140 mg/dL), % high (>140 mg/dL), % low (<64 mg/dL), and severe low % (<54mg/dL) and coefficient of variation (CV) and other statistical measures of glucose variability in those with CGM will be reviewed from the RT- CGM device data at baseline and visit 2-4. Blinded CGM values will be obtained at baseline and visit 2 and 3.

Glucose meter: Compliance with fingersticks 4 times a day will be recorded by average number of fingersticks per day. Glucose data including: average glucose, standard deviation, mean amplitude of glucose excursion (MAGE), time in range % (65 and 140 mg/dL), % high (>140 mg/dL), % low (<64mg/dL), and severe low % (<54mg/dL) will also be recorded.

N:Antenatal Ultrasound Markers: estimated fetal weight (in grams and percentile) using Hadlock scale, Biparietal Diameter, Head circumference, abdominal circumference, and femur length. Amniotic Fluid Index.

O: Delivery Outcomes:

Obstetric Outcomes:

- 1.Gestational age at delivery
- 2.Labor status (spontaneous labor, induced labor, no labor). For induced labor include indication for induction
- 3.Mode of delivery (vaginal delivery, cesarean delivery, operative vaginal delivery) including indication for delivery
- 4.Shoulder dystocia: defined as a delivery that requires additional obstetric maneuvers to release the shoulders after gentle downward traction has failed. SD occurs when either the anterior or, less commonly, the posterior fetal shoulder impacts on the maternal symphysis or sacral promontory

Maternal Outcome:

1. Preeclampsia or GHTN
2. Maternal insulin or medication use

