3. Maternal hypoglycemia: symptoms or asymptomatic biochemical hypoglycemia (fingerstick or RT-CGM less than 54 mg/dL (3.0 mmol/L), severe (fingerstick or RT-CGM < 64mg/dl (3.6 mmol/l)
4. Maternal weight gain

Fetal Outcome:

1. Gestational age at delivery
2. Live born or stillbirth

3. Birth weight: (large for gestational age, small for gestational age, macrosomia, birthweight ratio). Large for gestational age: birthweight > 90th centile for gestation using Fenton 2013 growth charts. Small for gestational age: birthweight below the 10th centile using Fenton 2013 growth charts. Macrosomia: birthweight ≥ 4 kg.
4. Birthweight ratio (birthweight adjusted for gestation and gender calculated with the Fenton 2013 web calculator (<http://peditools.org/fenton2013>)).
5. 5- minute Apgar score
6. Respiratory distress
7. Neonatal hypoglycemia: defined as < 4 h of life: < 1.4 mmol/l (30 min after first feed); < 2.2 mmol/l (1 h after subsequent feeds), 4–24 h of life: < 1.9 mmol/l (prefeed); < 2.5 mmol/l (1 h after feed)
8. NICU admission including LOS
9. Birth injury (such as brachial plexus injury)
10. Hypoxic ischemic encephalopathy

P. Risks and Side Effects:

There are various possible risks and side effects that a participant may incur as a result of this study. At the beginning of the study, when participants are administered the informed consent form by research staff, they will be informed that their participation is completely voluntary and will be informed of the risks and benefits. They are free to leave the study at any time and will not be penalized. Potential subjects will also be told that failure to participate in no way affects the usual care they would receive from their OB provider. Only after all questions have been answered, both study staff and the participant will sign and date the consent form.

It is very unlikely that there will be any adverse events

There are possible risks associated with the intervention activities, including the medical device, including:

- a. Less Likely (1% \leq Event Rate < 5%): CGM site infection or tape allergy (<1-2%) (41)
- b. Likely (5% \leq Event Rate < 10%): None
- c. More likely (Event Rate $\geq 10\%$): None

Risk to Participants:

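### Maternal Outcome 3 (Section O) and Section N attach the same two hypoglycemia cut-offs, 54 and 64 mg/dL, to opposite severity labels, so they grade readings of 54–63 mg/dL differently

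*Combined protocol and SAP*

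**What the plan says.** Section O (Delivery Outcomes), Maternal Outcome item 3, sets the outcome as "symptoms or asymptomatic biochemical hypoglycemia (fingerstick or RT-CGM less than 54 mg/dL (3.0 mmol/L), severe (fingerstick or RT-CGM < 64mg/dl (3.6 mmol/l". The biochemical cut-off is thus 54 mg/dL and the severe cut-off is 64 mg/dL.

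Section N (Glucose/CGM Data/Evaluation Measures) lists among its CGM measures the percentages "low (<64 mg/dL), and severe low % (<54mg/dL"). Its glucose-meter paragraph repeats the same pair with the same labels.

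Only one other place grades low glucose by urgency, the alert settings for the intervention group in Section J. If insulin is needed, the low alert is switched on with "the threshold set at 65 mg/dl [3.6 mmol/l]. In addition, the urgent low alert (55 mg/dl [3.1 mmol/l"]).

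The Data Analysis Plan in Section E covers the continuous measures: "For the statistical, hypothesis-testing examinations of HbA1C, fructosamine, CGM readings, and glycemic variability across key time points, we will conduct mixed models". It names no test of Maternal Outcome 3.

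**The concern.** Two sections of one plan use identical numbers with exchanged labels, and nothing in the text shown reconciles them. An analyst who codes Outcome 3 as printed and one who follows Section N would assign different severity to the same stored reading.

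Under the Outcome 3 wording, the severe category also contains the whole biochemical category, so the two grades cannot separate milder from more serious biochemical events. A published count of severe maternal hypoglycemia would then sit beside a severe low percentage with a different meaning. Hypoglycemia bears on safety and is the subject of Aim 6, so readers are likely to look at both.

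**Working it through.** **Inputs**

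- Outcome 3 (Section O): hypoglycemia below 54 mg/dL, printed as 3.0 mmol/L; severe below 64 mg/dL, printed as 3.6 mmol/L.
- Section N, for CGM and for the meter: low below 64 mg/dL; severe low below 54 mg/dL.
- Unit ratio from the plan's own diagnostic values in Section G: "1-hr 180 mg/dL (10.0 mmol/L"), so 180 / 10.0 = 18.0 mg/dL per mmol/L.

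**Step 1. Reproduce the printed unit pairs.**

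- 54 / 18.0 = 3.00, printed 3.0: agrees.
- 64 / 18.0 = 3.56, printed 3.6: agrees.

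Each mmol/L figure belongs to the mg/dL figure beside it. If only one unit had been mistyped, the other would still show a different order. Here both units carry the same labels, so a unit slip does not explain the difference. The unclosed brackets do not change which number goes with which label.

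**Step 2. Grade a reading under both sections.**

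| Reading (mg/dL) | Outcome 3: hypoglycemia (<54) | Outcome 3: severe (<64) | Section N: low (<64) | Section N: severe low (<54) |
|---|---|---|---|---|
| below 54 | yes | yes | yes | yes |
| 54–63 | no | yes | yes | no |
| 64 and above | no | no | no | no |

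**Step 3. Read off the sets, taking readings in whole mg/dL.**

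- Hypoglycemia but not severe, Outcome 3: below 54 and not below 64. This set is empty.
- Severe but not hypoglycemia, Outcome 3: below 64 and not below 54. This is 54 to 63, or 63 − 54 + 1 = 10 values.
- Low but not severe low, Section N: the same 10 values.
- Severity grade differs between the sections: the same 10 values. Below 54 and from 64 upward, the two sections agree on severity.

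In mmol/L to one decimal the result is the same: no value is below 3.0 without also being below 3.6, and 3.0 to 3.5 is severe without being hypoglycemia.

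**The case against.** The best case on the other side is that this is a drafting transposition with little consequence. It concerns one maternal outcome, the sample size rests on HbA1c, and Section E attaches no test to the item. CGM and meter data are downloaded, so events can be regraded later without loss. All of this stands, and it limits the size of the point. It does not remove the contradiction, because an analyst still needs one rule.

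It can also be said that Section N defines percentages while Outcome 3 defines events, so the two need not match. But both apply their cut-offs to the same kinds of reading, fingerstick and CGM. Nor does the text shown give severe a separate meaning in Outcome 3, such as need for assistance. Listed appendices that are not shown, for example the adverse events log and the data and safety monitoring plan, might do so.

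Outcome 3 also mentions symptoms. If these are read as a criterion separate from the glucose value, a symptomatic event could still be non-severe. The empty-set result is therefore limited to biochemical events.

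A reader might go further and infer that the between-arm comparison is biased, because Outcome 3 counts fingerstick or RT-CGM values and does not name the controls' blinded CGM. The documents do not support that as an error. The text shown does not say which glucose record decides the outcome. Section H says that both arms give providers fasting and 1-hour post-meal values, and on that record detection would be roughly matched. It could be unequal if the fuller RT-CGM log or the continuous trace were set against control fingersticks, but no event rate is given from which to size this. Sections E and N already plan CGM measures in both arms.

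**Conclusion.** The contradiction holds on the face of the text and needs no clinical or numerical assumption beyond reading the labels as printed. It covers every reading of 54–63 mg/dL, ten whole-number values. That is the width of the band in dispute and not an effect size; how many participants would be affected cannot be estimated from the documents. HbA1c, the sample size and Section N's CGM measures are unaffected.

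It is tempting to conclude that Section N is right and that Outcome 3 misgrades severity, particularly as the device alerts (65 and 55 mg/dL) follow Section N's order. The documents show only that the two sections differ. The alerts are device settings with slightly different numbers, the 65 mg/dL alert is enabled only when insulin is required, and urgent is not defined as severe. They are context and do not settle which cut-offs the sponsor intended.

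**What to change.** Reconcile Section N and Maternal Outcome 3 so that the same cut-offs carry the same labels in both, and so that every severe event also meets the definition of hypoglycemia. The sponsor decides which cut-offs apply. The same edit could settle a reading of exactly 64 mg/dL, which in Section N is neither low (below 64) nor in range (65–140).

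The cost is a wording change. Grading should be done from the stored CGM and meter downloads, because severity labels abstracted earlier from records may reflect either rule. No new data are needed.

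Optional note, not a correction of an error: any between-arm comparison of biochemical hypoglycemia, including nocturnal hypoglycemia for Aim 6, is best made from CGM in both arms over the windows in which controls have it. Section J gives these: "The control group participants will wear the blinded CGM at beginning, at 30-32 and 34-36 weeks of the study". The first window is not an untreated baseline. Section H states that participants who qualify are allocated there and then ("they will be randomized into either the RT-CGM intervention or control arm at the screening visit"), and the intervention group starts RT-CGM at week 0. The downside is that intervention CGM days outside the three windows would be used only descriptively.
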